3.3. Withdrawal of Subjects from Study

Voluntary Withdrawal by Subject

Study participation is voluntary and subjects may withdraw at any point during the study. If a subject withdraws from the study, the investigator will make all reasonable efforts to determine the reason for the subject’s withdrawal and will document the reason on the applicable form and in the patient’s medical record. After a subject withdraws from the study, no effort will be made to replace or follow the subject. However, the subject will still be offered clinical management of their knee condition.

Withdrawal by Investigator

The investigator may withdraw subjects from the study for many reasons, including but not limited to the following:

- Occurrence of a serious adverse event
- Investigator’s discretion to withdraw subject for safety reasons
- Subject noncompliance with visits and/or assessments
- Subject is lost to follow-up (as defined below)

113
114
115
116
117
118
119
120
121
122
123
124
125
126
127
128
129
130
131
132
133
134
135
136
137
138
139
140
141
142
143
144
145
146
147
148
149
150
151
152
153
154
155
156
157
158
159
160
161

Lost to Follow-Up

Subjects will be defined as lost to follow-up when the following procedures have been documented in the subject's source documentation:

- At least 2 phone calls made on separate dates to the subject are not returned
- A letter is sent to the subject's last known address and the subject does not reply after 30 days.

4. Informed Consent

Investigators are responsible for obtaining and documenting the voluntary informed consent of the study subjects prior to conducting any study-related assessments per 21 CFR Part 50. Prior to beginning the trial the investigator must obtain written and dated approval of the informed consent form. Subjects will receive a copy of the initial signed and dated informed consent form prior to the subjects' participation in the trial and any revised informed consent forms during the duration of the trial.

The subject must sign and date the consent form in the presence of the investigator, who must sign and date the consent form in the presence of the subject. The communications with the subject regarding informed consent process (initial and subsequent) should be documented in the medical record.

5. Study Procedures

Study Assessments

Visit 1- Baseline Assessment

The following information will be collected at the time of enrollment:

- Informed Consent
- Medical History & Demographics

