- Patient Outcomes: Subject to complete VAS, VR-12, KOOS, Lysholm and SANE prior to injection.
- Range of Motion Assessment: Measurement taken using goniometer.

Visit 2- Randomization & Procedure

- **Inclusion/Exclusion review**
- **Randomization**
- Procedure: For patients with current knee effusion, the investigator will drain the effusion prior to the injection. For subjects that do not exhibit any signs of knee effusion, the investigator will proceed with the injection. Study subjects will be randomized to receive a cortisone or BioDRestore injection. Subjects will be blinded to the assignment. Prior to the injection, the area will be prepared with sterile solution and numbing agent. Next, an injection of one of the following treatments, dependent on randomization, will be injected into the articular space of the knee:

_2 cc of 40 mg/ml Kenalog with 3 cc of saline

_2 cc BioDRestore with 3 cc of saline

Knee arthrocentesis (for procedure, see below under "Follow-up Visits"): The study doctor will attempt to perform a knee aspiration to provide a delta value for the assay.

Follow-Up Visits (6WK, 3M, 6M, 12M)

The following information will be collected at each follow-up visit:

- 162 • Patient Outcomes: Subject to complete VAS, VR-12, KOOS, Lysholm, and SANE scales
163 • **6-month only, subject will return to the clinic for the following:**
164 ▪ Range of motion assessment
165 ▪ Knee arthrocentesis (aspiration): The area will first be prepared with sterile
166 solution and numbing agent. Using a 10-mL syringe, obtain at least
167 0.25mL of synovial fluid via a parapatellar approach. A knee aspiration
168 attempt will be made on all subjects that produced an adequate sample at
169 baseline prior to the injection. Upon completion, the syringe will be
170 labeled and transported to the Clemson Bioengineering Laboratory of
171 Orthopaedic Tissue Regeneration & Orthobiologics lab for analysis.
172 ▪ Aspirate analysis: Enzyme linked immunosorbent assay (ELISA) will be
173 performed on synovial fluid aspirated from the knees of study patients at 6
174 months post-injection to determine if there are quantitative differences in
175 soluble mediators and products of osteoarthritis. Briefly, synovial fluid
176 samples will be evaluated in duplicate for inflammatory (interleukin-1 beta;
177 IL-1 β and tumor necrosis factor-alpha; TNF- α), anti-inflammatory
178 (interleukin-1 receptor agonist; IL-1RA and interleukin-10; IL-10), pain

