179 (prostaglandin-E₂; PGE₂) and soluble signals which indicate cartilage
180 damage (S100A8 and S100A9 proteins, respectively).
181
182 Briefly, frozen (-80°C) samples will be thawed and analyzed using a
183 bicinchoninic acid assay (BCA) to normalize for total protein content.
184 Samples will be diluted accordingly using calibrator diluent supplied with
185 ELISA kits. ELISA will be performed according to manufacturer's protocols
186 and well plates will be analyzed optically on a μ -Quant microplate reader.
187 Concentrations will be determined using a standard curve developed from
188 known concentrations of supplied analyte. Experimental sample analyte
189 concentrations (ng/ml) will be plotted on histograms and group mean
190 concentrations \pm standard deviation will be calculated for each experimental
191 group.
192 • **12-month only, subject will return to the clinic for the following:**
193 ○ Range of motion assessment
194 ○ Radiographs of affected knee
195 • **Allowed Concomitant Medications and Prohibited Treatments**
196 ○ Concomitant Medications: Patients are allowed acetaminophen and/or ibuprofen
197 for the first 6 months following treatment.
198 ○ Prohibited Treatments: Oral steroids, steroid injections and Viscosupplementation
199 are not permitted for the first 6 months of the study in the treated knee.
200

201 6. Risk Analysis

202 *Potential Risks*

203 Mild pain and discomfort at the injection site are normal and expected reactions. While
204 rare, complications may occur due to either the cortisone injection or study injection.

205 These include the following:

- 206 • Infection
- 207 • Post-injection flare
- 208 • Localized subcutaneous or cutaneous atrophy
- 209 • Skin discoloration
- 210 • Stiffness

211
212
213
214
215
216
217
218
219
220
221
222
223
224
225
226
227
228
229
230
231
232
233
234
235
236
237
238
239
240
241
242
243
244
245
246
247
248
249
250
251
252
253
254
255
256
257
258

Potential Benefits

Participation in this study may offer no benefit to subjects. However, it is possible that the use of BioDRestore will result in better outcomes than corticosteroid when injected intra-articularly in patients with knee OA.

Study subjects will receive a \$50 stipend for each study visit for a total of \$300 if all visits are completed.

7. Adverse Events

Definitions

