An adverse event is defined as any untoward medical occurrence in a clinical investigation in which a subject is administered a study device and which does not necessarily have a causal relationship with the device. An adverse event can therefore be any unfavorable and unintended sign (including an abnormal laboratory finding or an abnormal radiographic finding), symptom, or disease temporally associated with the use of study device, whether or not related to the study device. The following are specific definitions of adverse events:

Adverse Event (AE) — any untoward medical occurrence in a subject, regardless if there is a relationship between the AE and the device.

Adverse Reaction (AR)- The FDA requires, per 21CFR 1271.350(a), the reporting of certain adverse reactions related to implantation, transplantation, infusion or transfer of an HCT/P. For tissue products, an Adverse Reaction is any unintended response, including a communicable disease, in the recipient of a human tissue or cell product implantation or transplantation. An Adverse Reaction is considered serious (SAR) if it meets the criteria of a Serious Adverse Event (see below).

Serious Adverse Event (SAE) — an adverse event that:

- leads to a death
- leads to a serious deterioration in the health of a subject that results in a life-threatening illness or injury
- results in a permanent impairment of a body structure or a body function
- requires in-subject hospitalization or prolongation of existing hospitalization
- results in medical or surgical intervention to prevent permanent impairment to body structure or a body function
- results in congenital anomaly/birth defect

Treatment for Adverse Events

In the event of an adverse event, the investigator and/or other professional personnel in attendance will provide whatever appropriate medical treatment is indicated for the problem.

Documentation of Adverse Events

All adverse events will be documented in the source documentation. Beginning after the study procedure has taken place, all AE's, including those measured, observed or volunteered, will be recorded on the applicable case report form. The investigator will review all documentation (e.g., hospital progress notes, laboratory, or diagnostic reports)

259 relative to the event being reported. The investigator will then record all relevant
260 information regarding an AE onto the study CRF.

261
262 The investigator will attempt to establish a diagnosis of the event based on signs,

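### Section 3.3 allows open-ended investigator withdrawal after a single injection and provides for no later questionnaires; separately, section 8 sets two deadlines for the same SAE report

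*Combined protocol and SAP*

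**What the plan says.** **Withdrawal.** Under Withdrawal by Investigator, section 3.3 reads: "The investigator may withdraw subjects from the study for many reasons, including but not limited to the following". The listed reasons are "Occurrence of a serious adverse event", the investigator's "discretion to withdraw subject for safety reasons", "Subject noncompliance with visits and/or assessments", and loss to follow-up. The text concerns leaving the study, not stopping a treatment. It does not say whether assessments go on.

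The one explicit statement about later follow-up is in a different paragraph of 3.3, Voluntary Withdrawal by Subject: "After a subject withdraws from the study, no effort will be made to replace or follow the subject".

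**Treatment and outcomes.** Section 5 gives one injection at Visit 2. At 6 weeks, 3, 6 and 12 months it requires: "Patient Outcomes: Subject to complete VAS, VR-12, KOOS, Lysholm, and SANE scales". These five scales are the primary endpoint in section 2. Neither section 5 nor the Schedule of Events provides for collecting them after withdrawal.

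**Analysis.** Section 11.1 plans an intention-to-treat analysis with multiple imputation by chained equations. It states no missing-data assumption and names no variables for the imputation model. Neither 11.1 nor 11.2 plans a sensitivity analysis.

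**Safety reporting.** Section 7 requires active follow-up of a subject with an adverse event until one of several end points is reached; study withdrawal is not among them. For the investigator's SAE report to the IRB, section 8 gives an outer limit of 10 working days in one paragraph and 48 hours in another.

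**The concern.** When treatment is given repeatedly, withdrawal can at least stop further exposure. Here, once the injection is given, no study dose is left to stop. Withdrawal then mainly ends assessments. A worry about a later procedure, such as the 6-month aspiration, is no reason to stop a form that the subject fills in.

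The permitted reasons are also not neutral. A serious adverse event, a safety judgment or poor attendance can each go with worse pain or function, which is what the primary scales measure. If tolerability or response differs between the arms, these withdrawals may differ too. An intention-to-treat comparison is strongest when outcomes are observed in everyone randomized. Each avoidable gap replaces an observation with a modelled value.

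The reporting text raises a different problem: a site cannot tell which section 8 deadline governs.

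**Working it through.** **1. The plan's own visit figure.** Section 6 gives $50 as the "stipend for each study visit for a total of" $300. The Schedule of Events has six visits (baseline, treatment, 6 weeks, 3, 6 and 12 months), and 6 × $50 = $300, so the figure reproduces. Four of the six are post-injection follow-ups.

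**2. Questionnaires lost per withdrawn subject.** Lost = remaining follow-up visits × 5 scales, out of 4 × 5 = 20. Stipend to retain the subject = remaining visits × $50.

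| Withdrawal occurs | Visits left | Questionnaires lost | Stipend to retain |
|---|---|---|---|
| Between injection and 6 weeks | 4 | 4 × 5 = 20 | 4 × $50 = $200 |
| After 6 weeks | 3 | 3 × 5 = 15 | 3 × $50 = $150 |
| After 3 months | 2 | 2 × 5 = 10 | 2 × $50 = $100 |
| After 6 months | 1 | 1 × 5 = 5 | 1 × $50 = $50 |

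**3. Which losses are avoidable.**
- Serious adverse event or safety: the questionnaires could usually still be asked for.
- Noncompliance: they could be asked for, but the return may be poor.
- Loss to follow-up: not obtainable.
- Unlisted reasons: unknown, because the list is open.

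**4. Bias.** The documents give no withdrawal rate by cause or by arm, so the bias in this trial cannot be computed. An illustration shows what it would depend on. Assume that withdrawn subjects differ from retained ones by *d* SD in both arms and that proportions *w*A and *w*B are withdrawn. Analysing retained subjects only, the arm difference is then biased by (*w*B − *w*A) × *d*. The inputs below are assumptions, not figures from the plan:
- gap of 10 points, *d* = 0.25: 0.10 × 0.25 = 0.025 SD
- gap of 20 points, *d* = 1.0: 0.20 × 1.0 = 0.20 SD
- equal withdrawal and equal *d*: 0

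The plan imputes rather than drops these subjects. Imputation would remove the part of such a bias that recorded data explain, and leave the part that depends on the unseen scores.

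**5. Section 8, side by side.** Both limits bind the same person (the investigator), the same event (an SAE) and the same recipient (the IRB). A report on day 5 meets the 10-working-day limit and breaks the 48-hour one. A further 10-working-day limit in section 8 covers the company's report to FDA, IRBs and investigators. That is a different step and not part of the conflict.

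**6. Section 3.3 against section 7.** Take a subject who withdraws voluntarily with an adverse event that has reached none of section 7's end points. Section 7 read alone requires continued follow-up; 3.3 read alone says no effort to follow. Section 3.3 does not mention adverse events, so it is unclear whether its sentence was meant to reach them.

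**The case against.** **The point rests on silence.** The investigator may withdraw subjects but need not, and the no-follow sentence is under voluntary withdrawal. This stands. A reader might infer that 3.3 forbids follow-up after investigator withdrawal; it does not. The finding is a gap, not a prohibition. Equally, the proposed change does not reach voluntary withdrawals, the one place where follow-up is expressly ended.

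**Blinding protects against arm-related withdrawal.** Section 3 keeps subjects and investigators blinded throughout, so the person deciding on withdrawal should not know the arm. This is a real safeguard. It does not prevent imbalance that arises because the injections differ in tolerability or effect.

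**Imputation already deals with it.** In part. Section 7 says "All adverse events will be documented in the source documentation", so such events could inform an imputation model. No recorded variable corrects for loss that depends on the unobserved score itself. A reader might infer that 3.3 contradicts intention to treat; it does not, since imputation keeps all 84 randomized subjects in the analysis. It weakens that analysis.

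**The avoidable loss may be small.** Loss to follow-up is outside the fix, noncompliant subjects may return little, and section 6 calls injection complications rare. This stands, and is why no large effect is claimed.

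**Power.** A reader might infer a power problem, because 20% loss leaves 84 × 0.80 = 67.2, below the stated minimum of 70. That shortfall comes from how 84 was obtained (70 × 1.2 = 84). It is a separate sample-size matter and no evidence about 3.3.

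**The reporting passages can be read together.** A report within 48 hours meets both section 8 limits, and a brief early notice followed by a detailed report is conceivable. But section 8 does not describe two stages, so the two outer limits still conflict as written. On 3.3 against section 7 the objection is stronger: 3.3 still offers withdrawn subjects care for the knee, and section 7 lets follow-up end by agreement. A flat contradiction is not supported; an ambiguity is.

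**Conclusion.** The concern holds as a low-cost improvement of unknown size. The protocol permits investigator withdrawal for an open-ended list of reasons after a single injection and makes no provision for later questionnaires. The resulting loss is partly avoidable and may be related to outcome. The amount ranges from 5 to 20 of the 20 post-injection questionnaires per subject withdrawn after injection and before the 12-month visit, depending on timing. How many subjects this affects, and any bias, cannot be derived from the documents; the 0.025 to 0.20 SD in the illustration rests wholly on assumed inputs and on an analysis of retained subjects only.

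The conclusion assumes that some subjects withdrawn for a serious adverse event, for safety or for other reasons would still complete a questionnaire if asked.

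Two separate points carry no weight for the main one. The section 8 deadlines are a genuine contradiction in wording. The 3.3 and section 7 texts are a minor ambiguity, confined to voluntary withdrawal with an unresolved adverse event.

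**What to change.** - **Section 3.3:** state that subjects withdrawn by the investigator for any reason other than loss to follow-up are asked to complete the remaining 6-week to 12-month questionnaires, unless they withdraw consent for data collection.
- **Section 11.1:** impute only what is still missing after that effort, and add a sensitivity analysis for departures from missing at random, for example a delta-adjusted imputation.
- **Section 8:** reconcile the two limits for the investigator's SAE report to the IRB.
- **Sections 3.3 and 7:** reconcile the no-follow sentence with the duty to follow adverse events.

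No view is taken on which reporting or follow-up rule is right.

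The cost is protocol wording, one further analysis, and a small collection effort with at most $200 stipend per retained subject. The number retained is unknown, so no total is given. Treatment, eligibility, sample size and the primary test do not change.

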29 a "morselized, flowable tissue allograft derived from amniotic tissues. Amniotic tissues have been shown
30 to support soft tissue repair, reduce inflammation and minimize scar tissue formation".^{6,7}

31

32 This study will compare corticosteroid injection to BioDRestore injection in patients with significant
33 (Kellgren-Lawrence grade 3-4) knee osteoarthritis. Our hypothesis is that BioDRestore will result in
34 better outcomes than corticosteroid when injected intra-articularly in patients with knee OA.

35

36 **2. Study Endpoints**

37

38 Primary Endpoint

- 39 • Visual Analog Score (VAS), VR-12, Lysholm, SANE and Knee Injury and Osteoarthritis
40 Outcome Score (KOOS) at the 6-week, 3-month, 6-month, and 12-month post-injection time
41 periods.

42

43 Secondary Endpoints

- 44 • Inflammatory markers at 6-months post-injection.

45

46 **3. Subject Recruitment and Screening**

47

48 *Screening*

49 Patients who present with osteoarthritis of the knee and are recommended for a knee
50 injection will be screened for inclusion into the study. Following discussion of the
51 study between the patient and the treating physician, the patient will be given the
52 opportunity to move forward with the informed consent process.

53

54 *Enrollment*

55 The subject will be considered enrolled once voluntary informed consent has been
56 given, and the form has been signed and dated by all required parties.

57

58 *Randomization*

59 Subjects will be randomized to a treatment arm (corticosteroid or BioDRestore injection)
60 using a 1:1 ratio. Once study eligibility has been confirmed, the study coordinator or
61 designee will randomize the subject to a treatment arm. The treatment for each subject
62 will be assigned through the study database.

63
64
65
66
67
68
69
70
71
72
73
74
75
76
77
78
79
80
81
82
83
84
85
86
87
88
89
90
91
92
93
94
95
96
97
98
99
100
101
102
103
104
105
106
107
108
109
110
111
112

Blinding

Study subjects and investigators will be blinded to the treatment assignment for the duration of the study to reduce the risk of bias. The research coordinator will provide the randomization to the investigator’s medical assistant (MA) prior to treatment in order for the MA to assist with preparation of the injection.

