372 2 groups and five outcome measures, and assuming an effect size of 0.20 (small) based on between group
373 differences we constructed a sample size estimation using a Multivariate Analysis of Variance
374 (MANOVA). Measuring global effects, with an expected 80% power, and a standard error of probability
375 of 0.05, we estimate the need for a minimum sample size of 70 for statistical significance (~35 per group).
376 To account for a 20% drop-out rate, a sample size of 84 subjects will be recruited. We will employ
377 intention to treat and a chains equation, multiple imputation method in which we will assign predictor,
378 structural and impute variables. Further, we will not oversample characteristics within each group for
379 drop-outs.
380
381

382 **11.2 Data Analyses**

383
384 Descriptive statistics will be used to describe both groups at baseline. Appropriate tests of differences will
385 be used to compare baseline differences in descriptive statistics, pain, range of motion, etc., between the
386 two groups (e.g., t-tests and chi-square). Adverse events, including severity of these events will be
387 captured and compared between the two groups. A Multivariate Analysis of Variance (MANOVA) will
388 be used to measure differences between the targeted outcome measure at each of the given timepoints
389 (baseline, 6-week, 3-month, 6-month, and 12-months post-injection time periods). A MANOVA
390 investigates the effects of a categorical predictive variable (groups) on 2 or more continuous outcomes,
391 which are correlated and represented by a vector of dependent variables. For all analyses, a p value of
392 <0.05 will be considered statistically significant.
393
394
395
396
397

398 **12. Bibliography**

- 399 1. Divine J, Zazulak B, Hewett TE. Viscosupplementation for knee osteoarthritis. Clin Orthop Rel
400 Res. 2006; 455:113-122.
- 401 2. Dawson J, Linsell L, Zondervan K, et al. Epidemiology of hop and knee pain and its impact on
402 overall health status in older adults. Rheumatology. 2004; 43:497-504.
403

404 3. Laupattarakasem W, Laopaiboon M, Laupattarakasem P, Sumananont C. Arthroscopic
405 debridement for knee osteoarthritis (Review). Cochrane Collaboration. Issue 4, 2009.
406 4. Younes M, et al. Systemic effects of epidural and intra-articular glucocorticoid injections in
407 diabetic and non-diabetic patients. *Joint Bone Spine*. 2007, 74(5): 472-6.

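### The pre-injection aspirate is taken for a delta value, but the assay, summary and secondary endpoint name only 6-month levels, so the plan is inconsistent about using the baseline sample

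*Combined protocol and SAP*

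**What the plan says.** Section 5, Visit 2, gives one reason for the pre-injection tap: the study doctor will "attempt to perform a knee aspiration to provide a delta value for the assay". The Schedule of Events agrees, marking knee aspiration at treatment and at 6 months.

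Section 5, Follow-Up Visits, restricts the second tap. An "attempt will be made on all subjects that produced an adequate sample at" baseline, before the injection. The required volume is at least 0.25 mL.

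The aspirate-analysis text, under the 6-month visit, says ELISA will be "performed on synovial fluid aspirated from the knees of study patients at 6" months after injection. Samples go through a "bicinchoninic acid assay (BCA) to normalize for total protein content". Analyte "concentrations (ng/ml) will be plotted on histograms and group mean" concentrations with standard deviations are then calculated for each group.

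The secondary endpoint in Section 2 is "Inflammatory markers at 6-months post-injection", and the Protocol Summary says the same. In Section 11.2 a MANOVA will "be used to measure differences between the targeted outcome measure at each of the given timepoints", and the timepoints listed are those of the patient-reported scales. The markers are not mentioned there.

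**The concern.** The stated purpose of the baseline sample and the stated handling of the markers do not fit together. A delta needs two assayed values per subject, and the rule for the 6-month tap makes best sense for paired samples. But the sentence that schedules the ELISA names one visit, the summary is of concentrations by group, and the endpoint is a level at one time. A laboratory and an analyst following those sentences would leave the baseline fluid unassayed and tabulate unadjusted 6-month levels.

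This affects the only secondary endpoint. A subject contributes only with an adequate baseline sample and a successful 6-month tap, so the evaluable set may be well below the 84 recruited, and the documents give no expected yield. In a small set, between-subject spread and chance baseline differences weigh heavily, and a baseline measurement is the obvious remedy. Leaving the use of baseline open also allows the choice between level and change to be made after the data are seen.

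**Working it through.** **1. The plan's own figure.** The only computed figure is the minimum of 70 subjects in Section 11.1, which assumes "2 groups and five outcome measures, and assuming an effect size of 0.20 (small) based on between group" differences. Reading 0.20 as f² in a MANOVA global test with 2 groups and 5 responses: df1 = 5, df2 = N − 6, noncentrality = N × 0.20, alpha 0.05. At N = 70 (df2 = 64, noncentrality 14) power is 0.801, so 70 reproduces. It concerns the patient-reported scales and says nothing about the markers.

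**2. The text side by side.**

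| Item | Where | Baseline used? |
|---|---|---|
| Purpose of Visit 2 tap | Section 5, Visit 2 | Yes, for a delta |
| Eligibility for 6-month tap | Section 5, Follow-Up Visits | Yes, adequate baseline sample needed |
| Fluid named for ELISA | Section 5, aspirate analysis | No, 6 months only |
| Summary statistic | Section 5, aspirate analysis | No, group mean ± SD |
| Endpoint | Protocol Summary, Section 2 | No, 6-month level |
| Inferential analysis | Section 11.2 | Markers not mentioned |

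No section says how a delta is calculated or compared.

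**3. What baseline could buy.** The documents give no correlation (rho) between baseline and 6-month values, no marker SD and no yield of adequate samples. These are assumed: rho 0.2 to 0.7, equal SD at both times, 10 or 20 pairs per arm.

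Variance of the arm difference, relative to the 6-month level alone (= 1):
- ANCOVA, large sample: 1 − rho²
- Change score: 2(1 − rho)
- ANCOVA with n pairs per arm: (1 − rho²) × (1 + 1/(2n − 4)). At n = 10 the factor is 1 + 1/16 = 1.0625.

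| rho | ANCOVA, large sample | ANCOVA, n = 10 per arm | Change score |
|---|---|---|---|
| 0.2 | 0.96 | 0.96 × 1.0625 = 1.02 | 1.60 |
| 0.3 | 0.91 | 0.91 × 1.0625 = 0.97 | 1.40 |
| 0.5 | 0.75 | 0.75 × 1.0625 = 0.80 | 1.00 |
| 0.7 | 0.51 | 0.51 × 1.0625 = 0.54 | 0.60 |

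In large samples the ANCOVA gain is worth 1/0.91 − 1 = 10%, 1/0.75 − 1 = 33% and 1/0.51 − 1 = 96% more pairs at rho 0.3, 0.5 and 0.7. Since 1 − rho² = (1 − rho)(1 + rho), it never exceeds 2(1 − rho). The change score is less precise than the 6-month level alone when rho is below 0.5.

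**4. In terms of power.** For an assumed difference of 0.5 SD with 20 pairs per arm (two-sided 0.05, normal approximation, large-sample variances, so slightly optimistic for ANCOVA), power is 35% for the 6-month level alone. It is 38%, 45% and 60% for ANCOVA, and 27%, 35% and 53% for the change score, at rho 0.3, 0.5 and 0.7.

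**5. Chance imbalance.** With 20 pairs per arm the SD of the chance baseline difference is √(2/20) = 0.32 SD. At rho 0.5 an imbalance of that size shifts the unadjusted 6-month difference by 0.5 × 0.32 = 0.16 SD.

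**The case against.** The strongest reply is that baseline use was clearly intended. The Visit 2 text speaks of a delta and refers to the follow-up arthrocentesis procedure, which includes sending the syringe to the laboratory. The 6-month tap is conditioned on a baseline sample. The ELISA text sits under a bullet for the 6-month visit, which may be why it names only that visit, and its later sentences about samples are not tied to one. This stands. A reader might infer that the sponsor decided to discard the baseline sample; the documents do not support that. They show an inconsistency.

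Other stronger readings also fail:
- **That every analysed subject has a baseline value.** The 6-month rule ensures an adequate baseline sample. A value exists only if that sample is assayed, which the ELISA text does not schedule.
- **That the arms will be tested on raw 6-month levels.** No between-arm marker test is specified, only a descriptive summary, and samples are normalised for total protein. The levels are unadjusted for baseline, not raw.
- **That the unadjusted comparison is biased.** The baseline sample precedes the injection, so selection on it should not depend on the treatment received. Under 1:1 randomisation the unadjusted difference is imprecise, not biased.

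It can also be said that a 6-month-level endpoint is defensible, since a change score does worse when rho is below 0.5, and that ANCOVA gains little in a very small subset. Both are right. The first is an argument against a plain delta, not against baseline as a covariate; the second limits the size of the benefit.

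**Conclusion.** The concern holds as an internal inconsistency. The plan takes a baseline sample for a delta, but the assay, summary and endpoint refer only to 6-month levels, and no marker analysis is specified. Read literally, the baseline sample goes unused.

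The size is conditional. At assumed correlations of 0.3 to 0.7, ANCOVA would cut the variance by 9% to 49% in large samples. With about 10 pairs per arm the cut at 0.3 is about 3%, and at 0.2 there is none. What is gained is precision and protection from chance imbalance. The correlation, the marker SD and the number of pairs are all absent from the documents.

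The point concerns a secondary endpoint and leaves the primary MANOVA and the sample size untouched. It should be settled before any sample is assayed. Multiplicity across the seven analytes is a separate point.

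**What to change.** - **Assay (Section 5):** state that ELISA is run on both the baseline and the 6-month sample of each subject with a pair.
- **Analysis (Section 11.2):** for each analyte, compare arms on the 6-month concentration by ANCOVA with arm and baseline concentration. Use the log scale if the data are skewed, with a rule for values below detection fixed in advance. Report the estimate with its 95% CI and the number of pairs per arm.
- **Endpoint (Protocol Summary, Section 2):** say that the 6-month level is compared with adjustment for baseline. With baseline as covariate on the same scale, level and change give the same arm difference, so any delta can be shown descriptively.
- **Visit 2 text:** one sentence has the investigator go straight to the injection when there is no effusion; another has an aspiration attempted without that distinction. These must be reconciled, because they determine how many pairs exist.

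The cost is plan wording and the assay of baseline samples that the protocol already collects. No new patient procedure is needed. In a very small subset the covariate may return little or nothing.
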